### **Eligibility Criteria**

To be eligible, stakeholders must meet the following criteria:

#### *Inclusion:*

- Employed in a HCW role (not previously enrolled in the study), a leadership role, a policymaking role, or other administrative/supervision role for an organization associated with the COPC teams with whom this study partnered (e.g., partner non-profit organization, affiliated clinics, Department of Health)
- 18 years or older (expected for all employed in the abovementioned positions)

#### *Exclusion:*

- Unable or unwilling to complete informed consent and study procedures (i.e., brief training(s), brief self-report assessments) in English, isiXhosa, or Afrikaans

## **Recruitment**

### **3.1.4 COPC HCWs: Recruitment**

Based on ongoing conversations with the Western Cape Department of Health, we will select two of the four COPC teams to partner with for this study. These teams will be located at two of the following four sites: Asanda, Nomzamo, Ikhwezi, Lwandle.

All members of the two chosen partner COPC sites will be invited to join the study. Study staff will work with COPC supervisors to determine an appropriate time to approach the COPC members, tell them about the study, and ask them if they are interested in participating. Due to the nature of the study procedures (i.e., group COPC training delivered during normal work hours), HCWs colleagues will know whether they participate in the training. However, we will make it clear that colleagues will never see each other's answers to assessment questions. We will also work with the supervisors to ensure that participation, or lack thereof, will not affect the HCWs employment.

### **3.1.5 COPC Patients: Recruitment**

After receiving the ETAU training (i.e., SU psychoeducation and screening), HCWs in both COPCs will be asked to screen their HIV patients for SU using the CAGE. HCWs will be trained on these screeners during ETAU training. If a participant screens positive on alcohol or other drug use (AOD), the HCW will ask the patient if they would be willing to be contacted by a researcher at the SAMRC about potentially participating in the study. If the patient says yes, the CHW will pass on any relevant contact information (e.g., phone number, address) to the study team. If a HCW on a COPC chooses not to screen a patient, they will be told they can still tell the patient about the study, and ask the patient if they would like to be contacted by a researcher at the SAMRC about potentially participating in the study. If the patient says yes, the CHW will pass on any relevant contact information to the study team. Finally, HCWs will be given study flyers that they can choose to hand out to their patients. These flyers have study contact information so that interested patients can contact the study team directly.

It will be made clear to all potential patient participants that joining or not joining the study will in no way affect treatment from their COPC HCWs, from their clinic, or from anyone else.

### 3.1.6 Stakeholders (Qualitative Interviews): Recruitment

NGO leaders, policymakers and other stakeholders (n=15) referred from health system leadership will be recruited. Trained study team members will approach stakeholders and tell them further about study procedures and ask if they would be interested in participating in a qualitative interview.

## Study Procedures

### 3.1.1 COPC HCWs: Procedures

Study procedures for HCWs in the Pilot PRC Study are described below and illustrated in Figure 1.

**HCW Enrollment and Baseline Assessment:** Eligible and interested HCWs in the two partner COPC teams will be enrolled upon completed the informed consent process. All HCWs will then complete an individual baseline assessment consisting of self-report measures to assess basic demographic and job information, and stigma towards SUD (*primary*).

**COPC Randomization & Training.** After all HCW baseline assessments have been completed, one COPC will be randomly assigned to the ETAU condition (i.e., ETAU training only) and one COPC will be randomly assigned to the Siyakhana (i.e., ETAU and PRC integration training) condition. These trainings are described in more detail below.

[figure not shown]
Randomization will be determined by flipping a coin on a video-call with multiple study staff members (including at least one PI) in attendance.

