## 1. OVERALL AIM AND SPECIFIC OBJECTIVES

### 1.1 Overall Aim

The overall aim of this study is to assess the feasibility, acceptability, and preliminary effectiveness of integrating peer recovery coaches (PRCs) into Community Oriented Primary Care (COPC) teams to help people living with HIV (PLWH) and problematic substance use (SU) better engage in health care.

PRCs are lay people with lived SU experience who are trained to help people with current SU problems. They have been lauded as an innovative, acceptable, and cost-effective strategy for supporting SU outcomes in some high-income settings. PRC models are scaling in the US, but their implementation in HIV care in low- and middle-income countries (LMICs) has been limited. To adapt a PRC model to this context, we previously conducted qualitative interviews with stakeholders and patients about their attitudes towards integrating PRCs into COPCs (Protocol ID #EC046-10/2020). From these interviews, we were able to assess barriers and facilitators to this integration, which informed our development of a draft model. We then conducted workshops with stakeholders and patients (Protocol ID #EC049-11/2021) to obtain stakeholder feedback on our proposed model. Based on workshop feedback, we then further adapted the model and received confirmatory feedback on the final proposed model. In the present study, we propose to test this final co-designed model by comparing health care engagement outcomes for PLWH and SU who are seen by a COPC with an integrated PRC to those who are seen by a matched COPC without an integrated PRC.

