### 1.2 Specific Objectives

To evaluate the feasibility, acceptability, and preliminary effectiveness of this PRC COPC integrated model (called “*Siyakhana*”), we will:

1. **Primary:** Evaluate the pilot effectiveness of *Siyakhana* reducing healthcare worker stigma towards substance use (SU), compared to a control condition (COPC enhanced treatment as usual (ETAU)):
  - a. Healthcare worker stigma towards SU at the three-month follow-up, measured using the Social Distance Scale (SDS;  $n=30$ )
2. **Secondary:** Evaluate the implementation of *Siyakhana* using the following measures:
  - a. Feasibility and Acceptability (COPC perspective)
    1. Feasibility and Acceptability subscales of an adapted Implementation and Dissemination measure, completed by healthcare workers (HCWs) in the *Siyakhana* condition at the six-month follow-up ( $n=15$ )
    2. Semi-structured qualitative interviews with HCWs in the *Siyakhana* condition after the six-month follow-up ( $n=15$ )
3. **Other:** Additionally evaluate the following outcomes using the following measures:
  - a. Feasibility and Acceptability (patient perspective)
    1. Feasibility and Acceptability subscales of an adapted Implementation and Dissemination measure, completed by patients (HCWs) in the *Siyakhana* condition at the three-month follow-up ( $n=25$ )
    2. Semi-structured qualitative interviews with patients in the *Siyakhana* condition after the six-month follow-up (up to  $n=25$ )
  - b. Feasibility and Acceptability (other stakeholder perspectives)
    1. Semi-structured qualitative interviews with key stakeholders (e.g., policymakers, organization and clinic heads, etc.,) at the end of the study (up to  $n=15$ )
  - c. Pilot effectiveness of *Siyakhana* patients (intervention) re-engaging in HIV care, compared to patients in the ETAU (control) condition, over three-months
    1. Patient engagement in clinic-based HIV care between baseline assessment and three-month follow-up assessment from medical records (dichotomous yes/no)

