### 3. Research Work Plan

#### Aims:

The overall aim of this study is to examine the feasibility, acceptability, and preliminary effectiveness of our adapted PRC-COPC model “Siyakhana”. The main goal of this model is to increase engagement in HIV care for PLWH with SU and decrease HCW stigma towards SU.

Using a pilot hybrid Type 1 effectiveness-implementation design, we will explore whether our adapted Siyakhana model is feasible, acceptable, and potentially beneficial for improving engagement in health care for PLWH with SU, and reducing SUD stigma among HCWs. We will compare two matched COPC teams (i.e., similar in HCW makeup and patient population). Both COPC teams will provide treatment as usual, which we will enhance by providing a brief psychoeducational training on SU and SU screening (enhanced treatment as usual; ETAU). One of the COPC teams will also be randomized to receive the PRC model integration (described more below).

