### Effectiveness Outcomes

#### 4.1.1 Primary Outcome: HCW Stigma Towards SU

HCW stigma towards SUD will be measured using the Social Distance Scale (SDS), a well-validated measure of stigma used to capture health-related stigma across conditions and has been recommended for assessing mental health stigma among healthcare providers.

A total SDS score will be calculated to represent HCW stigma towards the target population at each time point, with higher scores indicating greater desire for social distance. First, we will conduct descriptive analyses (e.g., mean, standard deviation) to summarize the CHW stigma, using the continuous SDS score. The data distribution will be assessed to see whether the underlying assumptions are met (e.g., normality). Then we will examine the trajectory of HCW SUD stigma scores over time across the two conditions using a generalized linear mixed model, which includes all data points. The primary parameter of interest will be the interaction between time and condition to test whether changes in SUD stigma over time differ between the two groups.

Data will be analyzed over both three-months (3MFU) and six-months (6MFU). The primary timepoint is the 3MFU.

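### With one COPC team per condition, the primary time-by-condition test compares two teams; its worker-level standard error and p-value do not test the Siyakhana effect in objective 1

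*Combined protocol and SAP*

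**What the plan says.** The design is stated openly. The overall aim compares patients of a team with an integrated peer recovery coach to "those who are seen by a matched COPC without an integrated PRC". The Aims paragraph of section 3 says "We will compare two matched COPC teams (i.e., similar in HCW makeup and patient population". Under COPC Randomization & Training, "one COPC will be randomly assigned to the ETAU condition (i.e., ETAU training only) and one COPC will be randomly assigned to the Siyakhana" condition, and "Randomization will be determined by flipping a coin on a video-call with multiple study staff members".

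Objective 1 (section 1.2) is to evaluate the pilot effectiveness of Siyakhana in "reducing healthcare worker stigma towards substance use (SU), compared to a control condition". Section 4.1.1 answers it "using a generalized linear mixed model, which includes all data points", and adds: "The primary parameter of interest will be the interaction between time and condition to test whether changes in SUD stigma over time differ". It also says "The primary timepoint is the 3MFU".

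Section 4.1.2 compares patient engagement in HIV care between the groups by logistic, Poisson and Cox regression. The only power statement is for that outcome, in the rationale for patient enrolment numbers: about 85% for 24% versus 66%, with 50 patients and up to 20% attrition or missing records. Section 4 mentions no team effect, clustering or intraclass correlation (ICC), and no limitation arising from one team per condition.

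**The concern.** One coin flip decides which of two teams receives the peer recovery coach. Any team-specific change over the following three to six months (staff turnover, a new supervisor, a local event) falls wholly on one condition, and the model cannot tell it apart from an effect of the coach. The enrolment rationale itself expects staff to leave and new staff to be hired.

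The model will still return a standard error and a p-value for the interaction. Both are built from variation between workers and within workers over time. Read as an answer to objective 1, they assume without saying so that the two teams would otherwise have changed by the same amount. Section 8.1.1 plans to publish preliminary effectiveness findings, so someone who followed the plan exactly could report a significant Siyakhana effect that the design cannot support. The patient comparisons share the problem, and have no baseline value of the outcome to subtract.

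**Working it through.** **Inputs.** From the documents: 2 teams and 2 conditions; about 15 workers per team (minimum 30 in total), with the largest team at about 24; patient rates of 24% and 66%; 50 patients less 20%, so 20 analysed per team. Assumed, because the documents state neither: a two-sided 5% level, and ICCs of 0.01, 0.02, 0.05 and 0.10.

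**1. The plan's own power figure.** With 20 per team and independent patients, the unpooled standard error is √[(0.24×0.76 + 0.66×0.34)/20] = √(0.4068/20) = 0.1426. Then 0.42/0.1426 = 2.945, and Φ(2.945 − 1.96) = Φ(0.985) = 83.8%. Exact binomial enumeration of the unpooled test gives 84.6%. The stated figure of approximately 85% is reproduced, but only by treating patients as independent with no team effect.

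**2. What the primary interaction estimates.** The expected difference in change between the teams is (Siyakhana effect) + (team-specific change in one team − team-specific change in the other). Subtracting baseline removes stable differences in level between teams. It does not remove the second bracket.

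**3. Degrees of freedom.** Team-level df = 2 teams − 2 conditions = 0. A random team-by-time term cannot be separated from the condition-by-time effect. A randomization test has only 2 possible allocations, so its smallest p-value is 1/2 = 0.50 one-sided and 1.0 two-sided, however many workers are enrolled.

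**4. How large a team difference would matter.** In a two-sample test on change scores, p = 0.05 is reached at a difference of t(0.975; 2m − 2) × √(2/m) standard deviations of the change score:
- m = 15: 2.048 × 0.365 = 0.75 SD
- m = 24: 2.013 × 0.289 = 0.58 SD

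These are ordinary critical differences. They show the size of team-specific change that would produce significance with no Siyakhana effect, not how likely it is.

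**5. Illustration with assumed ICCs.** Let the change score have within-team ICC ρ. The true variance of the contrast exceeds the worker-level variance by u = [1 + (m − 1)ρ]/(1 − ρ), and the rejection rate under no effect is 2 × P(t₂₈ > 2.048/√u). With m = 15:

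| Assumed ρ | u | Rejection rate |
|---|---|---|
| 0.01 | 1.14/0.99 = 1.15 | 6.7% |
| 0.02 | 1.28/0.98 = 1.31 | 8.4% |
| 0.05 | 1.70/0.95 = 1.79 | 13.7% |
| 0.10 | 2.40/0.90 = 2.67 | 22.0% |

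This t test is a proxy for the planned model, whose random effects and time coding are not specified. A simulated three-occasion mixed model with a random worker intercept and complete data gave 6.8%, 8.5%, 14.0% and 22.7% for the 3-month interaction, and 5.1% at ICC 0.

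For patients (20 per team, 24% in both teams, pooled z test, beta-binomial enumeration) the corresponding rates are 7.4%, 9.8%, 16.8% and 26.4%, against 5.1% if patients are independent.

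**The case against.** The strongest reply is that nothing in section 4.1.1 is false. It proposes to test whether change differs between two groups, and as a comparison of these two teams that test is valid. The design is disclosed repeatedly, the study is called a pilot of effectiveness and not efficacy, its effect size is called preliminary, and section 5.1.10 leaves a powered assessment to later versions. The teams are matched. Their clinics are about 1.5 km apart in the same larger community, and one nonprofit oversees both teams, so some outside events would affect both. The error rates rest on ICCs that nothing in the documents supports; at 0.01 the rise is only from 5% to 6.7%.

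Much of this stands. A reader might infer that the comparison is worthless or the design concealed; neither is so. A reader might take 22% as this trial's false-positive rate; the documents give no basis for choosing any value in the range. A reader might conclude that the power figure is wrong; it is reproduced, and it belongs to an outcome classed as Other.

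What does not stand is that the caveats cover the point. They concern precision and power, and more workers in the same two teams would leave the confounding unchanged. Matching and proximity may make team-specific change smaller but supply no replication. Nowhere do the documents say that condition and team cannot be separated.

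**Conclusion.** Section 4.1.1 is wrong as written when used to answer objective 1. The interaction is a sound estimate of the difference in SDS change between two named teams. Its standard error and p-value are valid for a Siyakhana effect only if team-specific change is zero, an assumption that the plan neither states nor defends. This follows from one team per condition and needs no ICC. The 6.7% to 22% range illustrates size only, under assumed ICCs of 0.01 to 0.10, 15 workers per team and a two-sided 5% level. The same limit applies to the three patient models in 4.1.2. It matters more than a missing detail would, because following the plan to the letter permits a significance claim about Siyakhana that the data cannot carry.

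**What to change.** - **Section 4.1.1:** state that, with one team per condition, condition is completely confounded with team. Report the interaction as the difference in SDS change between these two teams, with a confidence interval described as conditional on these teams. State that neither a p-value nor an interval excluding zero will be presented as evidence of a Siyakhana effect.
- **Section 4.1.2:** make the same statement for the logistic, Poisson and Cox comparisons.
- **Objective 1 (section 1.2):** align the wording with what is estimated.
- **Rationale for patient enrolment numbers:** add that the approximately 85% power assumes independent patients and no team effect. The figure itself need not be restated.

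This costs a few sentences. It needs no extra teams, participants or data, and the model and estimate stay as planned. The downside is that the trial gives up a significance claim about Siyakhana, which one team per condition could not have supported.

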#### ETAU Training (Psychoeducation):

Both COPC teams will receive the ETAU training from our study team. This training will consist of psychoeducation around how to screen and refer for SU in HIV patients, the prevalence of SU in HIV, and the impact SU has on HIV care. This training will last for 1-2 days, depending on COPC availability. A brief psychoeducation refresher course (i.e., one afternoon a week or two after the original training) will also be offered. The purpose of this refresher will be to review how to screen and refer patients for substance use and answer any questions about screening and referring.

**PRC Integration Training:** Only the COPC randomized to the Siyakhana (PRC+ETAU) condition will receive the Siyakhana PRC Integration Training. In this training, the already trained PRC will be introduced to HCWs in the Siyakhana COPC. Together, the PRC and these HCWs will be trained on the PRC role (i.e., the difference between a PRC and a CHW) and how to refer to the PRC. This

Figure 1. HCW Procedures

training will last from 1-2 days, depending on COPC availability. After the training, the PRC will join this COPC (e.g., shadow team members before patients are enrolled, work closely with the COPC team, attend weekly COPC supervision) for the remainder of the study.

**Active Treatment Phase:** After the training(s), HCWs in both COPCs will continue visiting and treating patients as usual. The treatment as usual will potentially be enhanced (i.e., ETAU) by HCWs now being trained in how to screen patients for SU, and how to refer patients to local, publicly-funded SU treatment programs. The study team will provide each COPC with initial SU screeners, and let the COPCs know that the team can provide more screeners at any time during the active phase of the study.

**Siyakhana:** HCWs in the Siyakhana COPC will be aware that any patients who enroll in the study will be invited to meet with the PRC. This PRC will be present at COPC meetings, supervisions, etc.

**HCW 3MFU:** Approximately three-months after the PRC integration (i.e., enrollment of first patient participant), all HCW participants will be asked to complete a three-month follow-up (3MFU) assessment. This brief assessment will consist of the same self-report stigma measures as the HCW baseline assessment.

**HCW 6MFU Assessment.** Approximately six-months after the PRC integration, all HCW participants will be asked to complete a six-month follow-up (6MFU) assessment. This assessment will consist of the same self-report stigma measures as the HCW baseline and 3MFU assessments. Additionally, HCW participants in the Siyakhana condition will be asked to complete the Feasibility, Acceptability, and Appropriateness subscales of an Implementation & Dissemination measure.

**Qualitative Interviews.** After the 6MFU assessment, all HCW participants in the Siyakhana condition will be invited to participate in a semi-structured, individual interview with a study team member. The purpose of this interview will be to assess the feasibility and acceptability of the PRC Model Integration. Ideally, these interviews will be conducted immediately after the 6MFU assessment. However, if it is not possible to conduct them on the same day as the 6MFU assessment, the interview will be scheduled for as soon as possible.

### 3.1.2 COPC Patients: Procedures

Study procedures for patient participants in the Pilot PRC Study are described below and illustrated in Figure 2.

**Patient Screening & Enrolment.** At least once a week, the study team will consult with enrolled COPC HCWs on patients who may be interested in participating in the study. The study team will contact these patients and briefly tell them about the study. If a patient is still interested in potentially participating, the study members will officially screen the patient. If the patient is still interested in participating after screening and met all eligibility criteria, a staff member will complete the informed consent process with the patient as soon as possible. The consent form will include all study procedures and state that we are seeking approval to extract information from medical records (i.e., information related to clinic visits (dates, attendance), HIV (viral load, CD4 count), care for other chronic diseases, referrals to other programs including SU treatment programs, etc.). It will also state that we are seeking approval to see if they attended local publicly funded SU treatment programs (date(s) of attendance, location(s) attended), provided through the South African Community Epidemiology Network on Drug Use (SACENDU). Finally, it will state that the study will only collect medical record and SU treatment program attendance data between the date of their baseline assessment and the date of 6MFU.

**Patient Baseline Assessment:** Upon completing informed consent, all patients will be asked to complete a self-report baseline assessment with a study team member. Ideally the baseline assessment will be completed immediately after informed consent is given. However, if the patient is unable to complete the baseline assessment immediately after consent, a time to complete the assessment will be scheduled for as soon as possible. The patient baseline assessment consists of self-report questions around demographics, SU, HIV, and stigma. After the baseline assessment, all patient participants will be given another referral to the nearest free SUD treatment program(s) (for example, the Help Me Network).

[figure not shown]
**Patient Active Treatment Phase: 0 to 12 weeks post-baseline.** Following the completion of the patient baseline assessment, the below procedures will occur.

**ETAU Patients.** Patients seen by the ETAU COPC will continue to receive normal treatment from their COPC HCWs (i.e., normal efforts to re-engage patients in HIV care). These normal visits will be enhanced through (1) their COPC HCWs knowing how to, and therefore, potentially screening them for problem SU, and (2) their COPC HCWs knowing how to give referrals to local SU treatment programs. It is also possible that they will receive enhanced care from their COPC HCWs due to their COPC HCWs now knowing more about SU in the context of HIV.

**Siyakhana (PRC+ETAU) Patients.** Patients seen by the Siyakhana COPC will be invited to attend sessions with a PRC after their baseline assessment.

The structure and content of PRC sessions were designed based on patient and stakeholder feedback about PRCs (Protocol IDs: EC049-11/2021, EC046-10/2020). Siyakhana patient participants will be invited to meet with the PRC on a regular basis for approximately 12-weeks (3-months). Each meeting will be scheduled to last approximately 30 minutes, although an hour will be allocated for each meeting. The PRC and patient together will decide where to meet in a venue that is physically and psychologically safe for both the PRC and patient. Options deemed safe by stakeholders and patient participants in our formative work included the library, the local clinic, community centers, and for some, their homes. The location that the PRC and patient chooses will be recorded so that we have this information for future iterations of this project. The goal of these meetings will be for the PRC to motivate the patient to return to HIV care and seek SUD treatment. In training the PRC, the PRC will have attained competence in providing brief education around SU and HIV, supporting the patient in their recovery, and helping the patient problem-solve barriers to accessing both HIV and SU care.

Figure 2. Patient Procedures

Frequency of PRC sessions, and an overview of their content, are described in the table below. The proposed contact schedule was co-designed with patient and stakeholder feedback in our formative work but is only meant as a guideline for the PRCs. While it is expected that most patients will follow the below structure, additional sessions can be added or removed if needed in this pragmatic implementation study. Similarly, while the PRC will be instructed to complete all sessions within the 3-month period after baseline, there can be some flexibility (e.g., if a patient is away for a month in December/January, they may have the option to pause sessions for a month and pick them back up in late January). The frequency that patients meet with the PRC, and the general content of each session, will be recorded and used to inform further refinements to the PRC model for future trials.

